## 7. Data Specimen Banking

No specimens will be collected as a part of this study. Trained study staff will assess the eligibility of participants using a database (Excel or REDCap). Data from study assessments will be directly collected in REDCap. Essential study staff will only have access to the REDCap project and their study roles will dictate what type of access they will have.

## 8. Sharing of Results with Participants

- Publication of study findings is expected, where data will be published in aggregate and without identifying study participants.
- A summary of the main study results will be emailed to participants upon completion of the study. These results will all be in aggregate and without identifying study participants.

## 9. Study Timelines

**Protocol Title:** Shift-and-persist and cardiometabolic markers among women in Puerto Rico: a pilot of a mindfulness-based trial

Each participant will participate in three study assessments and in the 4-week intervention. It is expected that each participant will be in the study for about 2-4 months, depending on the timing of the baseline assessment and the intervention initiation, and the timing of the 1-month post-intervention assessment.

**Study timeline**

Research Activity	Month 1	Month 2	Month 3	Month 4	Month 5	Month 6	Month 7	Month 8	Month 9
Study Recruitment wave 1 and baseline assessment	X								
Wave 1: 4-week intervention		X							
Study Recruitment wave 2 and baseline assessment		X							
Post-intervention assessment wave 1			X						
1-month post-intervention assessment wave 1				X					
Wave 2: 4-week intervention			X						
Study Recruitment wave 3 and baseline assessment			X						
Post-intervention assessment wave 2				X					
1mo post-intervention assessment wave 2					X				
Wave 3: 4-week intervention				X					
Post-intervention assessment wave 3					X				
1mo post-intervention assessment wave 3						X			
Data analysis					X	X	X		
Manuscript preparation and submission					X	X	X	X	X

## 10. Inclusion and Exclusion Criteria

### *Inclusion criteria*

- Reporting female sex at birth
- Not identifying as a man, trans man, or trans woman.
- Between the ages of 18-29 years
- Individuals residing in Puerto Rico
- Spanish speaking
- Currently not pregnant
- Elevated stress (defined as a score  $\geq 6$  in the Perceived Stress Scale (PSS-4))
- Willing to undergo research activities (focus group discussions).

### *Exclusion criteria*

- Male sex at birth
- Identifying as a man, trans man, or trans woman.
- Currently pregnant
- Previous participation in an 8-week MBSR program
- Younger than 18y or 30y or older
- Experiencing moderately severe or severe depressive symptoms (PHQ-9 > 15)
- Have active suicidal ideation (PHQ-9 item #9)
- Self-report history of cognitive and psychiatric conditions
- Lack of have access to internet/phone (mode of focus group discussions—via Zoom)

## 11. Population

We will exclude the following special populations:

- Adults unable to consent
- Individuals who are not yet adults (infants, children, teenagers)
- Prisoners
- Cognitively impaired or Individuals with Impaired Decision-Making Capacity
- Pregnant persons

We will not include vulnerable populations.

## 12. Local Number of Participants

We will enroll 30 women.

Given that 99.8% of individuals in Puerto Rico self-report as Hispanic, we expect to enroll Hispanic individuals.

## 13. Recruitment Methods

Spanish-speaking women between 18-29 y will be recruited through flyers posted/disseminated through social media (e.g., Instagram, Facebook, Twitter) and social pages/accounts. These pages are those from mentors and collaborators outside of Emory University given that Emory pages do not currently have the reach to the population in Puerto Rico. These pages include collaborators that have already worked with the PR in other studies and include: CienciaPR, PR-CEAL, Puerto Rico Public Health Trust, Ciencia en Tus Manos, Estudio PROSPECT, among others. Recruitment flyers will also be disseminated through newsletters and email blasts at academic organizations (not including Emory) including the University of Puerto Rico, Ponce Health Sciences University, and San Juan Bautista School of Medicine, among others.

---

**Protocol Title:** Shift-and-persist and cardiometabolic markers among women in Puerto Rico: a pilot of a mindfulness-based trial

---

Additionally, the printed flyer will be distributed (in-person) at community events, health fairs and billboards.

The study flyer includes a study email where interested individuals can contact the study staff for more information and to assess eligibility. The flyer also includes a QR code and its respective link to a Google Forms survey where interested individuals can enter their contact information. Specifically, the Google Forms survey only asks for 1) First and Last Name, 2) phone number and 3) email.

Interested individuals will provide verbal consent (see Verbal Consent document). Afterwards, individuals will be screened for eligibility via phone (see Screening Questionnaire). Data will be directly entered in the database (REDCap or excel). Screening questions include age, sex, gender, PSS-4, PHQ-9, history of cognitive and psychiatric conditions, prior participation in an 8-week MBR program, currently pregnant, and access to internet/phone:

- 1- Female sex at birth
- 2- Not identifying as man, trans man, or trans woman
- 3- Self-reported age = needs to be between 18-29y
- 4- Currently residing in Puerto Rico
- 5- PSS-4 score  $\geq 6$
- 6- PHQ-9 scores  $\leq 15$
- 7- A negative response to item #9 ("Thoughts that you would be better off dead, or thoughts of hurting yourself in some way?)
- 8- No self-reported history of cognitive and psychiatric conditions
- 9- Affirmative response on access to internet/phone
- 10- No prior participation in an 8-week MBSR program
- 11- Currently not pregnant

Eligibility will be assessed via stages, first through socio-demographic characteristics (age, sex, gender, pregnancy, place of residence). If the individual does not meet the socio-demographic criteria, then they will be notified that they are not eligible. If they do meet these criteria, they will go through the PSS scale and notified if they are eligible upon scoring their responses. Afterwards, they will complete the PHQ-9 and eligibility will be assessed and notified if they are not eligible. Lastly, questions on criteria #8-#10 will be asked and the participant will be notified of their eligibility status. The staged eligibility screening is done to reduce the number of people exposed to the PSS and PHQ-9 questions if they are not eligible according to the prior criteria. If eligible and interested in participating, the staff will send the REDCap link (via email or text, according to the participant's preference) leading to the electronic informed consent. The study personnel will describe the study protocol, discuss the informed consent, and answer any questions. Individuals will then fill out the electronic consent form and will be given access to the online baseline questionnaire (REDCap).

#### **14. Withdrawal of Participants**

Participants can leave a study at any time without penalty.

The person in charge of the research study, [name] [name], or any of the study representatives designated by her can remove a study participant due to lack of commitment to the

---

study, hostility or aggressive behavior towards study staff, study discontinuation, or changes in study protocols.

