#### **4. Study Endpoints**

##### **Primary endpoints:**

- Rates of recruitment and retention, adherence, and satisfaction. Adherence will be measured by the number of phone sessions attended and the frequency of self-reported completed home practice, both assessed at post-intervention assessments.
- Ratings of satisfaction, also assessed by survey in post-intervention assessments, will be measured with several questions, including one that reads “Overall, how satisfied were you with the stress reduction program”, “How satisfied are you NOW (after the stress reduction program) with your ability to manage the stress in your life?”, and “¿How much did the program helped you manage your stress?”
- We will also ask questions on satisfaction of the instructor and group setting: “Did you feel that the other participants cared about the group?”, “You felt that the instructor was very knowledgeable about the program”, “It was easy for you to communicate with the instructor”, and “Did you feel that the instructor cared about you?”

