#### **5. Study Intervention/Design**

This is a one-arm intervention study that will explore if a 4-week MBSR program is feasible and acceptable among young women in Puerto Rico with elevated stress. The intervention consists of 4 weekly virtual sessions and daily mindfulness exercises at home (between 5-16min of duration each, according to participant's availability). The participants will also complete three study assessments: baseline, post-intervention, and 1-month post-intervention. All study measures at all time points will be done online through questionnaires to be filled out by participants.

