provided and up to 10 reminders (via email, text or call) will be sent out to complete the assessment. The link to this last assessment will be sent out 1-month after completion of the intervention, but at least 3 weeks after the post-intervention assessment.

A weekly reminder will be sent out (the day prior to the session, via text and email) to remind participants to join the weekly Zoom call. Up to 10 reminders (on each occasion, via text, email or call) will be sent out to participants to complete the baseline, post-intervention, and 1mo post-intervention online questionnaire.

All gift cards will be electronic gift cards and the information will be sent out to participants via email or text.

Participants will be notified that all experiences shared during intervention sessions are considered confidential and should not be discussed outside of the group.

The following table shows the different measures being collected at the different time points (also see questionnaire/instruments provided for data collection at baseline, post-intervention, and 1mo post-intervention).

Timepoint	Baseline	Post intervention	1mo post intervention
Socio-demographics			
Age	X		
Gender	X		
Health insurance	X		
Education	X		
Income	X		
Municipality	X		
Food security	X		
SNAP	X		
Marital Status	X		
Perceived income	X		
Employment	X		
Mental health			
Depression (CESD-10)	X	X	X
PTSD (PCL-2)	X	X	X
Anxiety (GAD)	X	X	X
Perceived stress (PSS-4)	NA-included in screening	X	X
Resilience			
SP (Chen et al)	X	X	X
Mindfulness (FFMG-15)	X	X	X
Psychological flexibility (AAQ2)	X	X	X
Health behaviors			

PA (WHI)	X	X	
Perceived sleep qual	X	X	
Diet screener (Mattei et al)	X	X	
Emotional eating (TFEQ R18 V2)	X	X	X
Reward based eating (Reward based eating scale (RED))	X	X	X
Smoking	X	X	
e-cigarettes	X	X	
Clinical characteristics			
Self-reported diagnosis	X		
Medical care for mental health	X		
Medications for mental health	X		
Anthropometrics			
Self-reported blood pressure	X	X	X
Self-reported weight	X	X	X
Self-reported height	x	x	x
Self-reported pulse	x	x	x
Intervention			
Satisfaction		X	
Stress management		X	
Group and instructor environment		x	
Exercise that helped the most		X	X
Exercise most often practiced		X	X
# sessions attended		x	
Frequency of daily practice and duration		X	X
Overall feedback		X	

We have delineated a suicide prevention protocol as explained in section #19 of this document.

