
If using contests or raffles as an incentive, you must offer entry to all potential participants, not just those who enroll in the study/complete study-related procedures, per Georgia State Law.
 
If recruiting online, describe how potential participants would be directed to your recruitment information and study description.
 
All research recruitment through social media needs to follow this guidance, which does not allow the use of personal social media accounts for some recruitment activities
	

Withdrawal of Participants*: Describe anticipated circumstances under which participants will be withdrawn from the research without their consent. Describe procedures that will be followed when participants withdraw from the research, including partial withdrawal from procedures with continued data collection.
	 Yes

Risk to Participants*: List the reasonably foreseeable risks, discomforts, hazards, or inconveniences to the participants related to the participant's participation in the research. Include as may be useful for the IRB's consideration, a description of the probability, magnitude, duration, and reversibility of the risks. Consider physical, psychological, social, legal, and economic risks. Include risks of loss of privacy or breach of confidentiality.
 
If applicable, indicate which procedures may have risks to the participants that are currently unforeseeable.
 
If applicable, indicate which procedures may have risks to an embryo or fetus should the subject be or become pregnant.
 
If applicable, describe risks to others who are not participants.
 
Do not state that there are no risks.
	 Yes

Potential Benefits to Participants*: Describe the potential benefits that individual participants may experience
 
Indicate if there is no direct benefit. Do not include benefits to society or others.
 
Describe areas of knowledge that would be strengthened.
 
Compensation should NOT be stated as a benefit.
	 Yes

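### Removal for low commitment overlaps with the adherence and retention endpoints, and nothing says a removed woman is still surveyed, so low-adherence results could be selectively lost (minor)

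*Combined protocol and SAP*

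**What the plan says.** Section 14 allows women to leave at any time. It also provides that the investigator in charge, or a representative she designates, "can remove a study participant due to lack of commitment to the" study; the other listed grounds are hostile conduct, discontinuation of the study and protocol changes. It does not say what happens to data collection after a removal.

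Section 4 opens its primary endpoints with "Rates of recruitment and retention, adherence, and satisfaction". It defines adherence by sessions attended and by self-reported home practice, both taken at the post-intervention assessment, and places the satisfaction ratings in the post-intervention survey.

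Section 5 states: "All study measures at all time points will be done online through questionnaires to be filled out by participants". In the Section 6 table of measures, the row for "sessions attended" is marked at post-intervention only, as is satisfaction. The row "Frequency of daily practice and duration" is marked at post-intervention and at 1 month. Section 6 opens the post-intervention questionnaire after the last session and adds: "Up to 10 reminders (on each occasion, via text, email or call) will be sent out to participants" for each of the three assessments.

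Section 18 computes recruitment, adherence, retention and satisfaction on the total sample, without saying how removed women are counted. Section 19 has the principal investigator present at all four weekly sessions, to assess fidelity. Section 17 ties the $50 card to completing both the programme and the second assessment.

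**The concern.** The pilot exists to learn whether young women in Puerto Rico will take up and keep to a four-week programme. Section 7 of the table of contents aside, the Background itself names time commitment as a barrier in the earlier Puerto Rico study of this kind of programme. A woman who attends little is therefore a result of the study and not a nuisance to it.

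Section 14 allows that same behaviour to be a reason for removing her. If removal also ends the surveys, an observed low session count, low home practice and perhaps low satisfaction become missing values, and the loss depends on the outcome being measured. Retention would fall while adherence among those who answer would rise, so the endpoints would be affected in different directions.

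A related weakness does not depend on removal. If sessions attended are known only from the post-intervention survey, attendance is missing for anyone who does not answer it, whatever the reason.

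**Working it through.** **Inputs from the documents.** Enrolment is 30 (Section 12), which agrees with 3 waves of about 10 (Section 6): 3 x 10 = 30. There are 4 sessions (Section 5). The card values are $25, $50 and $25 (Section 17). The documents give no expected number of removals, dropout rate, adherence cut-off or target, so there is no plan figure to reproduce for this point.

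**Assumptions.** k is the number of women removed and not surveyed. d is the gap in mean sessions attended between the other women and those k women. I take k = 1, 2 or 4 and d = 1 to 3, and assume all the other women answer.

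**Step 1: what depends on the survey.** Home practice and satisfaction can come only from the woman herself. For attendance, Section 4 attaches the self-report label to home practice only, but Section 5 and the Section 6 table point to the questionnaire and no attendance log is named. The source of the session count is thus not fully settled. Steps 3 and 4 apply if it is the survey.

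**Step 2: retention.** One removal changes retention by at most 1/30 = 0.033, or 3.3 points, and by 0 if she would not have answered anyway. For scale, an assumed 27/30 = 90.0% has an exact (Clopper-Pearson) 95% interval of 73.5% to 97.9%, which is 24.4 points wide.

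**Step 3: mean sessions attended.** Let m_o be the mean among the others and m_r the mean among removed women.

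- Mean over all enrolled = ((30 - k) x m_o + k x m_r) / 30
- Mean over respondents = m_o
- Difference = k x (m_o - m_r) / 30 = k x d / 30

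| k | d = 1 | d = 2 | d = 3 |
|---|---|---|---|
| 1 | 0.03 | 0.07 | 0.10 |
| 2 | 0.07 | 0.13 | 0.20 |
| 4 | 0.13 | 0.27 | 0.40 |

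Check with k = 4, m_o = 3.5, m_r = 1.0: (26 x 3.5 + 4 x 1.0) / 30 = 95/30 = 3.17 against 3.50. The difference is 0.33 = 4 x 2.5 / 30.

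**Step 4: effect of a log.** With attendance recorded at each session, the count exists for all 30 women and the difference in Step 3 is 0, for removed women and for other non-responders alike. Home practice and satisfaction are not recovered this way; they need continued surveying.

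**The case against.** The strongest reply is that several undocumented steps separate the clause from any harm. The clause is permissive, and no text equates commitment with session attendance. Staff would have to use it for low attendance, stop surveying the woman, and do so to someone who would otherwise have answered. This stands: the point is a risk, and its frequency is unknown.

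Second, follow-up is not conditional on attendance. Section 6 offers the questionnaires and reminders to participants generally, so a low attender who is not removed is already followed. This also stands. A reader might infer that poor attenders as a group are lost, and the documents do not support that; the gap concerns formally removed women.

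Third, staff probably know who attended. The principal investigator is at every session, the $50 card presupposes some knowledge of who completed the programme, and the Section 5 sentence cannot be literal for recruitment and retention. This weakens the attendance part but does not remove it, because Sections 4 and 6 still time the count at post-intervention and name no log. It does not help home practice or satisfaction.

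Two stronger readings should be resisted. One is that adherence would be badly inflated. If 21 of 30 women were adherent (70.0%) and six low adherers were removed and left out, the figure would read 21/24 = 87.5%. That needs six removals, an adherence cut-off the documents do not give, and dropping the women from the denominator although Section 18 refers to the total sample. The other is that the undefined removal term, or the ticked checklist item in Section 28 asking for withdrawal procedures with continued data collection, shows a breach. The checklist text is a generic prompt, and the tick can mean only that the section is present. Both are missing detail and form no part of this point. The consent form is not in the material reviewed, so what it says about data after withdrawal cannot be checked.

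**Conclusion.** The point holds as a minor one. A removal ground overlaps with two primary endpoints, the measures concerned are placed in a post-intervention questionnaire, and nothing says a removed woman still receives it. Low-adherence results could be selectively lost.

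The expected size is small: at most 3.3 points of retention per removal, well inside sampling error at n = 30, and 0.03 to 0.10 in mean sessions for one removal. Larger values, up to 0.40, need four unsurveyed removals and a three-session gap. These figures rest on assumed values of k and d, on all the other women answering and, for sessions, on the survey being the only source. The case for a change rests on the loss being selective and cheaply avoidable, not on a large expected bias.

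**What to change.** 1. **Section 14.** State that removal from the programme for low commitment does not end data follow-up: the woman is still sent the post-intervention and 1-month questionnaires, with the existing reminders, unless she withdraws consent. This leaves the discretion over programme participation as it is.
2. **Sections 4 and 6.** Take sessions attended from a log kept at each Zoom session, which the principal investigator already attends, instead of from the post-intervention survey.
3. **Section 18.** Use all enrolled women as the denominator for retention and session attendance. Give the number responding for home practice and satisfaction. Report removals by reason, keeping administrative removals (study discontinuation, protocol changes) in the denominator but listing them separately.

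**Cost.** Wording in Sections 4, 6, 14 and 18, a simple log, and reminders for a few more women. Section 17 also needs a clarification of whether the $50 card is paid to a woman who answers without completing the programme. If it is, the cards cost at most $50 + $25 = $75 per woman kept in follow-up (4 women: $300), within the $100 per woman already planned. Adherence and satisfaction figures may come out less favourable.

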## **15. Risk to Participants**

There may be side effects from the mindfulness program that are not known at this time. The most common risks and discomforts expected in this study are the time commitment for the weekly sessions and the completion of the study assessments. The mindfulness intervention that is being tested may not work for study participants and they may not perceive any benefits from the intervention. Researchers may ask questions about stress and stress management that may upset some participants. Interviewers are trained on cultural sensitivity and how to minimize any discomfort, including handling sensitive questions and emotional reactions. We will provide a toll-free phone number that individuals may call for any emotional or psychological advice or referrals at any time (from Línea PAS). Línea PAS is a 24hr 365days/year phone line responding to individuals with suicidal behavior and mental health disorders. It offers crisis counseling and emotional support, screening, psychiatric and psychological evaluation, and referrals (all free of charge). In addition, information on resources to coordinate mental health services will be provided to all prior to completing the screening questionnaire (see Mental Health Services document). Lastly, as with any study collecting identifiable information, there is a risk of loss of confidentiality but every effort will be made to keep all personal information confidential by use of id codes, password protected data files and analysis of de-identified data. Data on criminal or civil records, or any sensitive or personal information that may lead to such, will not be collected.

